Heart Rate Variability Procedures. At Week 2, participants will be instructed to place the Polar H7 heart rate monitor around the center of their chest, in contact with the skin, and the ActiGraph wGT3X-BT around their waist, according to directions outlined in the written instructions provided and as demonstrated in the instructional video and practiced with the applicant over the phone. Participants will be informed that the monitors are used to gather data about their body at rest. The Polar H7 heart rate monitor connects to the ActiGraph with Bluetooth® wireless technology so that the interval between normal heart beats (RR data) can be transferred to csv files for analysis. The HRV protocol will take place during a 10-minute time period on two consecutive days, to ensure at least one 10-minute time frame of usable data. Participants will be instructed to place the monitors first thing in the morning after they wake up and empty their bladder. Once the monitors are placed, participants will be instructed to lay supine quietly for 10 minutes and avoid moving or using any devices or watching tv. The standardized HRV protocol improves reliability of the HRV measurement because control of extraneous variables is maintained. Respirations will not be controlled because this can artificially increase HF HRV. The gold standard amount of time for a short-term HRV recording is 5 minutes. The 5 minutes of the recording with the least amount of artifact will be used for analysis. After 10 minutes of recording are completed, the heart rate monitor and ActiGraph will be removed. After the participant completes the 10-minute HRV measurements on two consecutive days, they will be asked to return the monitors in a prepaid envelope that will be

picked up from their mailbox by USPS and returned to the PI, mitigating any exposure to COVID-19.

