Phone Visit to Complete Questionnaires. After completion of the HRV measurement instructional phone visit, participants will receive their Week 2 data collection visit. Participants in the PI's study will receive their phone visit from the PI. The PI will follow a script for data collection. Data collection interviews will take on average 20 minutes. During the phone visit, the data collector/PhD student will first ask how HRV measurement went that morning and remind participants to complete the measurement the following morning. Participants will then be asked to complete the four questionnaires indicated at the Week 2 timepoint in Table 1 (demographic questionnaire, State-Trait Hopelessness Scale, ENRICH Social Support Inventory, and Patient Health Questionnaire-9). Demographic data are being collected to describe the sample and determine if these variables are confounders. Depressive symptoms are being measured as a potential covariate because of the known association between hopelessness and depression.¹⁶ Upon completion of data collection, participants will be compensated \$20 for their time and commitment to the study. This is the same amount that patients enrolled in [name] study receive after their Week 2 visit. All questionnaire and electronic medical record data will be logged directly into REDCap using a secure electronic tablet. Data from medical records will be collected within 2 weeks of the participant's hospital discharge.

Measures. Characteristics of study measures appear in Table 1.

Table 1. Study Measures, Concepts, Variables, & Psychometric Properties

Measure	Concept	Time-point	# Items	Range	Description	Reliability/Validity
Polar H7 Heart Rate Monitor	Heart rate variability	Week 2	NA	Varies by domain	
 Monitor is worn across patient's chest to provide heart rate data Monitor has Bluetooth capabilities with ActiGraph WGT3X-BT so RR data can be transferred to csv files for analysis 	Strong correlation with ECG for measuring short-term HRV ($r=0.99$)
Demographic Questionnaire	Demographics	Week 2	17	NA	
 Age, sex, race, smoking status, ability to participate in physical activity, history of depression, marital status, education level, insurance status, employment status 	NA

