6.0 Expected Risks/Benefits

Potential Risks. There is minimal likelihood or seriousness of potential risks to participants. There are no identified physical, legal, or financial risks. Participants may become fatigued during completion of the study questionnaires and HRV monitoring and may feel apprehensive or distressed sharing information, but there is low probability of this and a low level of seriousness. There is potential for loss of confidentiality; however, procedures to protect against this risk will be put in place, as described below. Patients will continue to seek and receive standard medical care for their IHD diagnosis; therefore, any health care problems that may arise will be referred to their health care provider.

Protections Against Risk: The PI who will conduct remote data collection (by phone) 2 weeks after patients' hospital discharge, has been trained to assess for potential fatigue or apprehension of participants. If participants exhibit apprehension, they will be given the option to discuss this, to complete the questionnaires at another time, to be referred to their physician for further counseling follow-up, or to discontinue the study. These are all expected to be effective approaches. Patients will additionally be informed that they can withdraw from the study at any time, without loss of benefits they would otherwise be entitled to and without penalty to their health care. There is no risk for incidental findings.

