9.0 Quality Control and Quality Assurance

The PI is responsible for collecting and analyzing the data for the proposed study. HRV data will be analyzed as soon as monitors are returned to ensure proper data capture. Participants that do not have an appropriate HRV recording will be asked to wear again. The PI will ensure all data is entered accurately during each visit.

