11.3 Unanticipated Problems

Participants will be queried about potential adverse events and unanticipated problems as defined below:

Adverse event. An adverse event will be defined in this research as any untoward or unfavorable medical occurrence in a study participant, including any abnormal symptom (including psychological), sign (including physical), or disease temporally associated with the participant's involvement in the research, whether or not considered related to participation in the research. Adverse events in this study will include, but not be limited to, death, cardiac restenosis (myocardial infarction, revascularization with coronary artery bypass surgery or percutaneous coronary intervention), or suicidal ideation.

Unanticipated problem. An unanticipated problem will be defined in this research as any incident, experience, or outcome that meets all of the following criteria: 1) unexpected (nature, severity, or frequency) given the research procedures that are described in the research protocol and informed consent, and given the characteristics of the study population; 2) related

or possibly related (reasonable possibility that the problem may have been caused by study procedures) to participation in the research; and 3) suggests that the research places participants or others at a greater risk of harm (including physical, psychological, economic, or social harm) than was previously known or recognized. Unanticipated problems in this study will include, but not be limited to, a breach of confidentiality.

Adverse events and unanticipated problems will be monitored in several ways during the implementation of the study protocol. First, adverse events and unanticipated problems will be monitored by the PI during data collection. The PI will document any adverse events and unanticipated problems reported to them by participants and report these immediately to their advisor. Second, all patients will be provided a toll-free phone number to contact the PI directly if they have any issues or concerns to report

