We will now complete the questionnaires together. Please find the hard copy of the questionnaires that were shipped to you so that you can read along. To complete the questionnaires, I will read each question to you and have you state your answer. I will chart your answers in our computer system. Do you have any questions before we begin?

Demographics and Characteristics

The first questionnaire will have you answer questions about yourself. (Ask patient the questions in questionnaire and chart answers in REDCap)

Self-Assessment Questionnaire (Hopelessness)

For the next questionnaire, please note that the first set of questions asks how you feel “today (right now)”, and the second set of questions asks how you feel “typically (over time). Also note that some of the questions are worded in a positive manner, and others are worded in a negative manner”. (Ask patient the questions in questionnaire and chart answers in REDCap)

Suicidal Ideation Screening

To be completed only if participant scores 1.8 or higher on the self-assessment questionnaire

The next few questions I ask will be used to assess your safety. (Complete suicide ideation questions with patient and following instructions in the virtual suicide protocol based on patient risk level).

Patient Health Questionnaire (PHQ-9)

We will move on to the next questionnaire. Over the last 2 weeks, how often have you been bothered by any of the following problems? (Ask patient the questions in questionnaire and chart answers in REDCap)

Enriched Social Support Instrument

The next set of questions assesses how you view your social support. The scale ranges from none of the time to all of the time. (Ask patient the questions in questionnaire and chart answers in REDCap)

Serious Adverse Events and Adverse Events

At the end of every visit, I like to check in and make sure you have not experienced any of the following since the research staff talked with you in the hospital or after your discharge home. (Complete questions).

Return Monitors and Compensation

Thank you so much for your time today! Please remember to place the two monitors in the prepaid return envelope. You can place the envelope in your mailbox and the postal service will pick it up. Once I receive the returned monitors, I will send you \$20 to thank you for participating in the study.

Do you have any questions about how to return the monitors or any other questions about the study?

Thank you for participation in the study!

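### No scheduled adverse-event query follows the second HRV recording or any re-wear, and under the Appendix B1 script none follows either recording

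*Combined protocol and SAP*

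**What the plan says.** **The query.** Section 11.3 commits the study to querying participants about adverse events and unanticipated problems, without giving a time. It names two routes. The first is that "adverse events and unanticipated problems will be monitored by the PI during data collection". The second is a toll-free number that participants can use to reach the PI. The only place where the question is actually scripted is the end of the Week 2 call in Appendix B1. It opens "At the end of every visit, I like to check in" and asks for confirmation that participants "have not experienced any of the following since the research staff talked with you in the hospital or after your discharge home".

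**The recordings.** Section 5.0 states: "The HRV protocol will take place during a 10-minute time period on two consecutive days". On the order of call and recordings, Section 5.0 has the data collector "first ask how HRV measurement went that morning and remind participants to complete the measurement the following morning". Appendix B1 instead teaches monitor placement and runs the questionnaires on one call, and speaks of both mornings as still ahead.

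**After the call.** Section 9.0 has recordings checked when the monitors come back, and adds: "Participants that do not have an appropriate HRV recording will be asked to wear again". Appendices B1 and C2 describe the return of the monitors by mail and then the sending of $20.

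**The stated risk.** Section 6.0 says: "Participants may become fatigued during completion of the study questionnaires and HRV monitoring". It rates this as improbable and not serious, and identifies no physical risk.

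**The concern.** The adverse-event definition in Section 11.3 covers any unfavourable occurrence temporally associated with participation, whether or not it is thought to be related. A query meant to serve that definition should reach the end of participation. This one stops at the Week 2 call, before the recordings are finished.

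What is at stake is how a null safety report should be read. If the final report says that no adverse events arose from HRV monitoring, part of that result comes from the timing of the question, because some or all of the recordings had not yet taken place. Anything after the call depends on the participant choosing to telephone, which is a weaker form of ascertainment than being asked.

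**Working it through.** There is no statistical figure to reproduce. The check is a timeline: for each part of the document that orders the call and the recordings, count the planned recordings that come after the scripted query.

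**Inputs**
- Planned recordings per participant: 2, on consecutive mornings (Section 5.0).
- Participants recruited by the PI: 45 (Sections 1.0 and 5.0).
- Scripted adverse-event queries: 1, at the end of the Week 2 call, looking back (Appendix B1).
- Re-wears: requested after the monitors have been returned and the data checked (Section 9.0). No expected number is given.

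**The sources side by side**

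| Source | Recording 1 | Recording 2 | Planned recordings after the query |
|---|---|---|---|
| Section 5.0 | Same morning, before the call | Next morning, after the call | 1 of 2 |
| Appendix B1 script | After the call | After the call | 2 of 2 |
| Appendix C1 | Morning after the package arrives | The next morning | Not determined: C1 does not say when the questionnaires are done |
| Appendix C2 | Order relative to the call not stated | Order relative to the call not stated | Not determined |

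C1 asks the participant to telephone on receiving the package. If that call is the B1 call, C1 agrees with B1, but the document does not say that it is.

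**Re-wear.** C2 has the monitors returned after both wearings and the call. Section 9.0 triggers a re-wear only after that return. Every re-wear therefore follows the Week 2 query under either order.

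**Count for the 45 participants**
- Planned recordings: 45 × 2 = 90.
- After the query, Section 5.0 order: 45 × 1 = 45, or 45/90 = 50%.
- After the query, B1 order: 45 × 2 = 90, or 90/90 = 100%.
- Re-wears come on top, in a number the documents do not give.

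**Is there a later query elsewhere?** The script's reference to every visit does not supply one, because no visit after the recordings is described; the separate instructional phone visit in Section 5.0 comes before them. The general commitment in Section 11.3 gives no timepoint. The return of the monitors and the payment are described only as mailing and sending, with no conversation.

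**The case against.** The strongest case on the other side is that this hardly matters. The procedure is ten minutes of lying still with two surface monitors. Section 6.0 finds no physical risk and expects fatigue to be rare and mild. The adverse events that Section 11.3 lists by name are death, cardiac events and suicidal ideation. The Week 2 query covers the interval from hospital to call for these, and the script has a separate suicidal-ideation screen for participants scoring 1.8 or higher. All patients have a toll-free number. The count of 45 to 90 recordings is a count of exposures, not of events, and no event rate is available. All of this stands, and it is why the point is minor.

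Three stronger readings are tempting, and the documents do not support them.

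- A reader might infer that events during HRV monitoring are never asked about, or that the query covers only a period without study procedures. Under Section 5.0 the first recording precedes the call, falls inside the query window, and is asked about directly. Under either order the questionnaires, which Section 6.0 also names as a source of fatigue, come before the query.
- A reader might infer that unanticipated problems in particular will be missed. Section 11.3 requires three conditions together: unexpected, related or possibly related, and pointing to greater risk than was known. Fatigue during monitoring is already expected, so it would not ordinarily qualify.
- A reader might take Section 6.0 to mark HRV monitoring as a physical hazard. It says the opposite.

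What does not stand is that the toll-free number fills the gap. Section 11.3 offers it as a second route beside monitoring by the PI, and it relies on the participant to act.

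**Conclusion.** The point holds as a minor one. At least the second recording and every re-wear fall after the only scheduled adverse-event query; under the B1 script both recordings do. That is 1 or 2 of 2 planned recordings per participant. The commitment in Section 11.3 to query participants is therefore not carried through to the end of participation.

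The range of 45 to 90 comes from a separate inconsistency: Section 5.0 and Appendix B1 disagree on whether the first recording precedes the call. If Section 5.0 governs, what is left uncovered is one ten-minute resting recording per participant plus any re-wear.

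The conclusion assumes that each of the 45 participants has one Week 2 data collection call and makes both planned recordings, and that no later script exists beyond those listed in the appendices. Participants from the parent study are not counted, because its adverse-event procedures are not in this document. No harm is shown or expected, and no analysis under Aims 1 to 3 changes.

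**What to change.** 1. Reconcile Section 5.0 with the Appendix B1 script on whether the first recording comes before the Week 2 call, and state the same order in Appendices C1 and C2.
2. Keep the Week 2 query as it is for the period from hospital to call.
3. Repeat the same adverse-event questions once after the last recording, by text, call or REDCap link, when the monitors are received and before the $20 is sent. Define the window as running from the Week 2 call until the monitors were returned.
4. Ask them again after any re-wear, with the window extended to the second return.
5. State these timepoints in Section 11.3.

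The cost is one brief contact for each of the 45 participants, plus one for each re-wear, with some non-response to be expected. This is a new contact: receipt of the monitors and payment are administrative steps at which the document describes no exchange with the participant. No new staff, instrument or study procedure is needed.

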Appendix C

Participant Documents

C1: Written Instructions to Complete Heart Rate Variability Measurement

Placement of Two Monitors

Thank you for your participation in our research study. When you receive this package, please give me a call and I will instruct you on how to wear the monitors for the study. The instructions below describe the same process I will guide you through over the phone.

Please complete your wearing of the two monitors the first time on the morning after you receive the package. We ask that after you wake up, use the restroom, and then place the monitors and wear them for 10 minutes. In the bag you will find the two monitors. The monitor labeled Polar will need to be worn around your chest and in contact with your skin. Please open the ultrasound gel in the bag and place some on the inside part of the Polar monitor. This helps it connect better with your skin. Next, place the monitor around your chest and make sure it is tight enough so that it does not move. The piece that has Polar written on it should be in the front center of your chest. Next, place the red monitor around your waist. The two monitors should be worn as shown in the image below. A blue light should flash on the red activity monitor when both monitors are on correctly. If a blue light is not flashing, use your hands to warm the monitor around your chest until the blue light flashes.

Once both monitors are on correctly, please find a spot in your house where you feel comfortable lying flat on your back for 10 minutes, such as your bed or a couch. While lying down, please remain silent and try not to move for the 10 minutes. Once the 10 minutes is done, you can remove both monitors.

Complete this same process again the next morning. After you have worn the two monitors two times for 10 minutes, you can remove them a final time and place them in the prepaid return envelope.

[figure not shown]

Figure showing proper monitor placement.

Thank you!

C2: Directions to Return Monitors after Heart Rate Variability Measurement

Directions to Return 2 Monitors to Research Staff

After you have worn the 2 monitors for 10 minutes on two consecutive days and completed your phone visit with a data collector, please place the monitors in the return envelope. Shipping has been prepaid and the US Postal Service will pick up the envelope from your mailbox.

After you complete your phone visit with a data collector and research staff receive the returned monitors, you will be sent \$20 for completing the study.

Please do not hesitate to call with any questions.

Thank you for your participation in the study!

Appendix D

Data Collection Instruments

D1: State-Trait Hopelessness Scale

Self-assessment (State-Trait Hopelessness) Scale Part 1 of 2

DIRECTIONS: A number of statements, which people may use to describe their thoughts, are given below. Read each statement and then circle the response to the right of the statement that best describes how you are thinking today (right now). There are no right or wrong answers. All of your information will be kept confidential.

Today (Right now)...

1. Today, it is difficult for me to imagine my future.	Strongly disagree	Disagree	Agree	Strongly agree
2. Today, I believe I cannot make a difference.	Strongly disagree	Disagree	Agree	Strongly agree
3. Today, I believe that things will improve.	Strongly disagree	Disagree	Agree	Strongly agree
4. Today, I believe I am powerless to change my future.	Strongly disagree	Disagree	Agree	Strongly agree
5. Today, I see my future as gloomy.	Strongly disagree	Disagree	Agree	Strongly agree
6. Today, I believe I will accomplish what I set out to do.	Strongly disagree	Disagree	Agree	Strongly agree
7. Today, I believe I can help improve things.	Strongly disagree	Disagree	Agree	Strongly agree
8. Today, I feel giving up would be easier.	Strongly disagree	Disagree	Agree	Strongly agree
9. Today, I believe I can overcome obstacles.	Strongly disagree	Disagree	Agree	Strongly agree
10. Today, things will not work out as I would like.	Strongly disagree	Disagree	Agree	Strongly agree

Self-assessment (State-Trait Hopelessness) Scale

Part 2 of 2

DIRECTIONS: A number of statements, which people may use to describe their thoughts, are given below. Read each statement and then circle the response to the right of the statement that best describes how you typically think—or how you have thought over the years. There are no right or wrong answers. All of your information will be kept confidential.

Typically (Over the years)...

1. Typically, things do not work out as I would like.	Strongly disagree	Disagree	Agree	Strongly agree
2. Typically, I believe I can overcome obstacles.	Strongly disagree	Disagree	Agree	Strongly agree
3. Typically, I see myself as fortunate.	Strongly disagree	Disagree	Agree	Strongly agree
4. Typically, I see my future as gloomy.	Strongly disagree	Disagree	Agree	Strongly agree
5. Typically, negative things seem to happen to me.	Strongly disagree	Disagree	Agree	Strongly agree
6. Typically, it is difficult for me to imagine my future.	Strongly disagree	Disagree	Agree	Strongly agree
7. Typically, I believe I can help improve things.	Strongly disagree	Disagree	Agree	Strongly agree
8. Typically, I feel giving up would be easier.	Strongly disagree	Disagree	Agree	Strongly agree
9. Typically, I believe I will accomplish what I set out to do.	Strongly disagree	Disagree	Agree	Strongly agree
10. Typically, I believe that things will improve.	Strongly disagree	Disagree	Agree	Strongly agree
11. Typically, I believe I cannot make a difference.	Strongly disagree	Disagree	Agree	Strongly agree
12. Typically, I doubt that anything is worthwhile.	Strongly disagree	Disagree	Agree	Strongly agree
13. Typically, I believe I am powerless to change my future.	Strongly disagree	Disagree	Agree	Strongly agree

D2: ENRICHED Social Support Instrument

5-item ENRICHD Social Support Instrument

1	Is there someone available to whom you can count on to listen to you when you need to talk?	none of the time	a little of the time	some of the time	most of the time	all of the time
2	Is there someone available to you to give you good advice about a problem?	none of the time	a little of the time	some of the time	most of the time	all of the time
3	Is there someone available to you who shows you love and affection?	none of the time	a little of the time	some of the time	most of the time	all of the time
4	Can you count on anyone to provide you with emotional support (talking over problems or helping you make a difficult decision)	none of the time	a little of the time	some of the time	most of the time	all of the time
5	Do you have as much contact as you would like with someone you feel close to, someone in whom you can trust and confide in?	none of the time	a little of the time	some of the time	most of the time	all of the time

D3: Demographic Instrument

Demographics

1. What is your age in years?

2. What is your sex?

- (1) Female
- (2) Male

3. Are you of Hispanic or Latino origin?

- (1) Yes
- (2) No

4. What is your race?

- (1) White
- (2) Black/African American
- (3) American Indian or Alaska Native
- (4) Native Hawaiian or other Pacific Islander Asian
- (5) Other _____

5. What is your marital status?

- (1) Married
- (2) Separated
- (3) Divorced
- (4) Widowed
- (5) Never been married

6. Have you ever been diagnosed or treated for depression?

- (1) Yes
- (2) No

7. What is the highest grade of school or year of college you completed?

- (1) Eighth grade or less
- (2) Some high school
- (3) High school graduate
- (4) Some college
- (5) College graduate (bachelors)

- (6) Some post-graduate college work (masters, doctoral)
- (7) Graduate with masters- or doctoral-level degree

8. What is your current job status?

- (1) Employed full-time
- (2) Employed part-time
- (3) Retired
- (4) Disabled or unable to work
- (5) Student
- (6) Other (please list) _____

9. What type of health insurance do you have?

- (1) Medicare
- (2) Medicaid
- (3) Government VA
- (4) Employer provided
- (5) Privately purchased
- (6) No health insurance

D4: Patient Health Questionnaire

Patient Health Questionnaire (PHQ-9)

1. Little interest or pleasure in doing things	not at all	several days	more than half the days	nearly every day
2. Feeling down, depressed or hopeless	not at all	several days	more than half the days	nearly every day
3. Trouble falling or staying asleep, or sleeping too much	not at all	several days	more than half the days	nearly every day
4. Feeling tired or having little energy	not at all	several days	more than half the days	nearly every day
5. Poor appetite or overeating	not at all	several days	more than half the days	nearly every day
6. Feeling bad about yourself, or that you are a failure or have let yourself or your family down	not at all	several days	more than half the days	nearly every day
7. Trouble concentrating on things, such as reading the newspaper or watching television	not at all	several days	more than half the days	nearly every day
8. Moving or speaking so slowly that other people could have noticed? Or the opposite - being so fidgety or restless that you have been moving around a lot more than usual.	not at all	several days	more than half the days	nearly every day
9. Thoughts that you would be better off dead or of hurting yourself in some way	not at all	several days	more than half the days	nearly every day
10. If you checked off any problems, how difficult have these problems made it for you to do your work, take care of things at home, or get along with other people?	not difficult at all	somewhat difficult	very difficult	extremely difficult
